1.8 SAMPLE SIZE

1.8.1 HHS – primary endpoint

The primary endpoint will be collected among children aged 12-23 months included in the endline HHS about 12 months after the baseline HHS. Based on a baseline measles vaccination (i.e. at least one dose) coverage reported on vaccination card of 30%⁴, a power of 90%, and an intra-cluster correlation of 0.2, an alpha risk of 5%, it will be necessary to include 74 children per cluster. With a rate of unusable data of 5%, we will need 78 children per cluster or a total of 1,560 children to demonstrate a minimum of +10% points difference between the NutriVax and the standard EPI arms, in measles vaccination coverage, i.e. the primary outcome. This calculation was performed using the Shiny CRT calculator used specifically to estimate sample size for cluster randomised trials⁵.

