1.3 Study design

This NutriVax-Measles study will consist in conducting a pragmatic parallel cluster randomized trial (PCT) with baseline measure with different populations and data collection modes: 1) a baseline and an endline cross-sectional household surveys (HHS) of children aged 12-23 months, 2) a longitudinal 12 months follow-up household survey (LS) of children aged 6-12 months at inclusion, 3) two cross-sectional Qualitative Feasibility and Acceptability Survey (QFAS) of parents/legal guardian of children aged 6-23 months, health care providers, community health workers, 4) caregiver cost survey (CCS) of the caregivers of children from the longitudinal cohort (population 2), and 5) a health facility cost survey of a randomized sub-sample of health facilities.

Thanks to these different data collection modes, measles vaccination coverage and the quantitative secondary endpoints will be measured both at the community level using the endline HHS and at the individual level using the LS (Figure 1).

The NutriVax program will be assessed within a routine program implemented at scale. PCT pragmatic studies are designed to guide decision-making in the real-world clinical practice and policy settings while maintaining the strengths of individual randomized controlled trials if they are systematically designed and performed properly. The pragmatic attitude increases external validity to ensure that the results can be generalized in everyday practice in this context and other similar settings^{2,3}.

The unit of randomization (i.e. cluster) will be a ward and its catchment area. We will include exhaustively all wards of each LGA where the study will take place.

[figure not shown]

Figure 1. Study design chart.

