1.6 Study sites

Research and operational activities will take place at community level and in the 20 PHCCs of the 2 LGAs of Karasuwa and Nguru LGAs. Each LGA has 10 wards and there is one PHCC per ward.

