1.7 Randomisation

The unit of randomization (cluster) will be the ward and its catchment area.

Randomization will be stratified by LGA in order to promote balance of the intervention among both LGAs and to give the same opportunity to receive the intervention in both LGAs. Also, the two LGAs may have different populations or contexts that could be a potential confounding factor.

Randomization will be done prior to the baseline survey, because of logistical constraints required for preparing SQ-LNS distribution at health centres (PHCCs), but kept concealed to the data collector until the completion of the baseline survey. After baseline survey completion, the study will be open, as it will not be possible to blind participants or study staff to SQ-LNS supplementation.

In each LGA, the 10 wards will be randomized the same day, by lottery from an envelope, in presence of PHCC department, local community representatives and held in the local language (Hausa). Clusters will be randomly allocated at a ratio of 1:1 either to the standard EPI arm or to the NutriVax arm.

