1.8.3 Precision

These two estimates were validated by the senior statistician for this study but they may need to be adjusted thereafter according to the actual intra-cluster correlation coefficient and the baseline measles vaccination proportion results from the baseline survey.

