3.1.2 Baseline measles vaccination coverage

The baseline coverage level will be calculated globally, by LGA, by cluster, by arm :

$$\frac{\text{Number of participants with endpoint}}{\text{Number of participants responding to the HHS}}$$

When used for the analyses, it will be affected to all participant belonging to the same ward, under the likely hypothesis that all participant in the ward area do not attend another ward.

We will estimate the baseline ICC and its 95% CI from our data by performing various calculations using the R ICCbin library⁷ or R ICCest library. First, we will use the Anova estimator (option R ICCbin ci.type=aov), that is originally proposed for continuous data but that is also used for binary data⁸. Then, we will use the Fleiss-Cuzick estimator that is a kappa-type estimator (option R ICCbin ci.type=fc) and the Pearson estimator that is based on direct calculation of the correlation between observations within each cluster (option R ICCbin ci.type=peq). If the results are different, we will keep the more conservative calculation, so the highest ICC estimator.

If necessary, we will refine thereafter the sample size of the endline cross-sectional survey according to the actual intra-cluster correlation coefficient and the baseline measles vaccine coverage proportion results from the baseline HHS survey.

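### The 90% power from 74 children per ward needs a cluster auto-correlation of 1, which the SAP never states; without a stated value, the highest ICC cannot be called conservative

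*SAP*

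**What the plan says.** Section 1.8.1 sizes the endline household survey on 30% card-reported measles coverage, a 10-point difference, 90% power and 5% alpha. It continues: "an intra-cluster correlation of 0.2, an alpha risk of 5%, it will be necessary to include 74 children per cluster". Allowing for 5% unusable data, this becomes 78 per ward and 1,560 in total. The calculation is attributed to the Shiny CRT calculator.

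The design is described in 1.3 as a "pragmatic parallel cluster randomized trial (PCT) with baseline measure". On clusters, 1.6 says "Each LGA has 10 wards and there is one PHCC per ward" for two LGAs, and 1.7 says "Clusters will be randomly allocated at a ratio of 1:1", so there are 10 wards per arm. The primary model in 3.4.1.1 adjusts for each ward's baseline coverage and uses a Kenward-Roger correction.

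The sizes are open to revision. Section 1.8.3 says "they may need to be adjusted thereafter according to the actual intra-cluster correlation coefficient" and the baseline coverage. Section 3.1.2 plans three ICC estimators and, if they differ, "we will keep the more conservative calculation, so the highest ICC estimator"; the endline sample may then be refined.

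**The concern.** A two-period cluster design has a correlation input besides the ICC: how closely a ward's true coverage at baseline tracks its true coverage a year later. With few clusters and a large ICC, this input largely determines power, because it sets how much between-ward variance the baseline adjustment removes. Section 1.8.1 does not give it, although 1.8.2 does give an individual auto-correlation for the cohort.

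Two things are at stake. First, a reader of a non-significant primary result would take the trial to have had 90% power for 10 points, when that rests on wards not shifting relative to one another over 12 months. The plan itself treats cold-chain days and measles vaccine stock days as ward factors worth adjusting for. Second, the re-sizing rule labels one direction of the ICC as safe, but which direction is safe depends on the missing input.

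**Working it through.** **Inputs from the SAP.** Coverage 30% versus 40%; ICC ρ = 0.2; two-sided 5% alpha (2.3.2); 10 wards per arm; m = 74 analysable children per ward.

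**Assumptions of this check.** The same m at baseline and endline, equal ward sizes, risk-difference scale, no gain from LGA stratification. CAC values below 1 are also assumptions, since the SAP gives none.

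**Formulas.**
- r = mρ·CAC / (1 + (m − 1)ρ)
- DE = (1 + (m − 1)ρ)(1 − r²)
- Var = (0.3×0.7 + 0.4×0.6)·DE / (10m) = 0.45·DE / (10m)
- Power = Φ(0.10/SE − 1.96). The bracketed version uses a non-central t with 20 − 3 = 17 df (intercept, arm, baseline coverage).

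**Reproducing the plan's figure (CAC 1).**
- 1 + 73×0.2 = 15.6; r = 14.8/15.6 = 0.949; DE = 15.6×(1 − 0.900) = 1.56
- Var = 0.45×1.56/740 = 0.00095; SE = 0.0308; 0.10/0.0308 = 3.25
- Power = Φ(3.25 − 1.96) = 90.1%; 74 is the smallest m reaching 90%
- 74/0.95 = 77.9, so 78; 78×20 = 1,560

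All three figures reproduce. With 17 df, power at 74 is about 86%.

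**Changing only the CAC (m = 74).**

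| CAC | Power, ICC 0.2 (17 df) | Power, ICC 0.05 |
|---|---|---|
| 1.00 | 90% (86%) | 87% |
| 0.99 | 85% (80%) | 86% |
| 0.95 | 66% (61%) | 82% |
| 0.90 | 51% (46%) | 77% |
| 0.80 | 35% (32%) | 68% |

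The ICC 0.05 column uses the normal approximation.

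**Can more children make up the loss?** At ICC 0.2, 90% power needs 74 per ward at CAC 1, 91 at 0.99 and 922 at 0.95. At CAC 0.90 it cannot be reached. As m grows, Var tends to 0.45×0.2×(1 − 0.81)/10 = 0.00171, so SE = 0.0414 and power tops out at Φ(2.42 − 1.96), about 68%.

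**The ICC rule.** Children per ward for 90% power at CAC 1:

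| ICC | 0.01 | 0.05 | 0.10 | 0.20 | 0.30 | 0.40 |
|---|---|---|---|---|---|---|
| m | 66 | 82 | 81 | 74 | 66 | 56 |

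The requirement peaks near ICC 0.07 and then falls. Below CAC 1 the direction changes: at CAC 0.95 and m = 74, power is 75% at ICC 0.1, 66% at 0.2 and 58% at 0.3.

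The two effects can combine. Re-sizing at ICC 0.4 with CAC 1 gives 56 per ward at a nominal 90%; if the CAC were 0.95, power at 56 would be about 49%.

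**The case against.** The strongest reply is that nothing in 1.8.1 is miscalculated: 74, 78 and 1,560 all follow from a recognised method. That stands; the fault is an undisclosed assumption, not an arithmetic slip. Section 1.8 also sits in a summary of the protocol, and the protocol may list the full calculator inputs. That softens the charge of omission, but not the sensitivity of the 90% figure or the 3.1.2 rule, which is the SAP's own.

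Several stronger readings are tempting and not supported:

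- **That true power is about 18%.** An endline-only comparison gives DE = 15.6 and roughly 18% power. That is not the planned analysis: 1.3 and 3.4.1.1 show that the baseline is used.
- **That power is 35% to 66%.** Those figures belong to CAC 0.80 to 0.95 at ICC 0.2. The SAP supplies no such range; power is 85% at CAC 0.99, and the loss is milder at lower ICC.
- **That the highest-ICC rule works backwards in general.** It does so only at or very near CAC 1 and above an ICC of about 0.07. At CAC clearly below 1, the highest ICC is the demanding case.
- **That the survey has been or will be shrunk.** Section 3.1.2 says only that the size may be refined if necessary, using coverage as well as ICC.

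It is also fair to say that one baseline survey cannot estimate the CAC, so a range has to be assumed. And the SAP already requires 95% confidence intervals, which show directly whether 10 points is excluded.

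**Conclusion.** The concern holds in limited form. The 90% power in 1.8.1 depends on crediting the baseline, which can be inferred from elsewhere in the SAP, and on CAC = 1, which cannot. Even granting both, the planned small-sample inference gives about 86%. At the planning ICC, a CAC of 0.95 would take power to about 66% (61% with 17 df) and 0.90 to about 51% (46%). These are conditional figures, not estimates of this trial's power.

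Calling the highest ICC conservative is unsafe without a stated CAC. Put into the calculation that produced 74, an ICC of 0.3 or 0.4 would reduce the requirement to 66 or 56. The conclusion rests on the linear-scale approximation and equal survey sizes set out above. Using a pooled variance instead moves the CAC 1 requirement only from 74 to 75.

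**What to change.** In 1.8.1, state that the calculation credits the baseline survey and takes CAC = 1. Add a short table of power at the planned size over a labelled range of CAC and ICC, using the planned small-sample degrees of freedom; its most favourable entry at ICC 0.2 would be about 86%.

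In 3.1.2, replace the choice of the highest ICC with a re-evaluation of power across the ICC estimates crossed with that same CAC range. Say that the endline size will not be reduced because a higher ICC is entered at CAC = 1. Where no number of children reaches 90% with 20 wards, report the attainable power instead. Section 1.8.3 should refer to this rule.

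The cost is SAP wording and one table. No extra children are requested, and the endpoint and model are unchanged. The price is a less favourable stated power.

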1.8.2 LS - Main secondary endpoint

The main secondary endpoint will be collected among the children aged 6-12 months at baseline included in the LS. Based on the baseline measles vaccination coverage reported on vaccination card of 30%⁴, a power of 80%, and an intra-cluster correlation coefficient of 0.2, an individual auto-correlation of 50%, an alpha risk of 5% and a rate of unusable data of 5%, it will be necessary to include 30 children per cluster or 600 children in total to demonstrate a minimum of +10% points difference between arms in measles vaccination coverage. This calculation was performed using the Shiny CRT calculator used specifically to estimate sample size for cluster randomised trials⁵.

1.8.3 Precision

These two estimates were validated by the senior statistician for this study but they may need to be adjusted thereafter according to the actual intra-cluster correlation coefficient and the baseline measles vaccination proportion results from the baseline survey.

2 STATISTICAL ASPECTS

2.1 STUDY SAMPLES FOR ANALYSIS

2.1.1 Intention-to-treat sample

Baseline HHS was already carried out in all randomised clusters by the time this SAP was written. All randomised clusters will be included in the planned analysis.

All individuals with available endpoint data will be included in the planned analyses.

2.1.2 Per-protocol sample

All individuals with available endpoint data and meeting criteria for study participants, as defined in section 1.4, will be included in the planned analyses.

2.2 STATISTICAL APPROACH

Variables will be described overall, by arm, by arm and by LGA, by arm and by cluster using appropriate summary statistics for the variable type. For quantitative variables, means, standard deviations, medians, interquartile ranges, and ranges values will be given. Data may be transformed or normalized as necessary based on review of the data distribution.

For qualitative variables, absolute numbers and percentages will be given, and 95% binomial proportion confidence intervals (CI) will be calculated; the exact method will be used when appropriate.

Categorical and discrete data may be aggregated into classes depending on frequency. Statistical testing between arms or subgroups will be carried out using the appropriate statistical test for the variable type (χ^2 , corrected χ^2 or the Fisher's exact test for categorical variables, depending on the observed frequencies and Student's t test, Kruskal Wallis test or the Wilcoxon test, depending on the distribution for continuous variables).

2.3 CALCULATION CONVENTIONS FOR STATISTICAL ANALYSES

2.3.1 Missing data management

For the cross-sectional survey with endpoints using data reported on vaccination card, we have 1 type of missing data: children without vaccination card.

For the longitudinal with endpoints using data reported on vaccination card, we have 2 types of missing data: children without vaccination card and children loss-to-follow-up.

For the longitudinal with endpoints using data reported on vaccination card or recall we have 1 type of missing data : children loss-to-follow-up.

We will describe these missing data.

For all endpoints using data reported on vaccination card, if the children don't have a vaccination card then vaccination will be considered as failure.

For the longitudinal survey, at first, analyses will be performed on available data only, so without loss-to-follow-up. The endpoint will be measured at the end of follow-up, so a child may be loss-to-follow-up at M12, but at the end of follow-up may have received vaccine, and therefore be considered as in success for an endpoint.

A particular case is that of a child who does not have a vaccination card at inclusion and who has a vaccination card during follow-up, so if he is vaccinated during follow-up, he will be considered as a success.

In addition, we will perform sensitivity analyses to assess the potential impact of missing data on the study conclusions, using the most extreme scenarios (like described in chapter 3.4.2.2).

2.3.2 Type I error

We will use a two-sided type I error α of 5% to compare endpoints between arms without any correction for multiple comparisons.

2.3.3 Statistical significance

The level of statistical significance will be $p < 0.05$, and estimates will be reported together with their 95% CI.

2.4 SOFTWARE

We will use either SAS Enterprise Guide version 8.3 or higher, or R software versions 4.2.2 or higher to prepare datasets, and conduct statistical analyses.

2.5 REPORTING

We will follow the Consort 2010 statement: extension to cluster randomised trials⁶ for reporting the results of the following analyses, including reporting ICC of the primary endpoint.

3 ANALYSES PLAN

3.1 CLUSTER CHARACTERISTICS

3.1.1 Before baseline cross-sectional survey

The following characteristics of clusters collected before the baseline cross-sectional survey will be described between arms, between LGA, between LGA*arm*clusters.

- Number of villages

- Population
- Number of Households
- Number of days with no cold chain
- Data aggregated of OPD (Out-patient department): total consultation of children aged 12-59 months ; and OTP (Out-patient therapeutic program) register: total number of children 6-59 months admitted.
- Data aggregated of IYCF register: total number of mothers of child 6-23 months sensitized on IYCF practices.
- Data aggregated of Health facility nutrition/growth monitoring and promotion register: total number of children 6-59 months receiving Vitamin A; total number of children 12-59 months receiving deworming

3.1.2 Baseline measles vaccination coverage

The baseline coverage level will be calculated globally, by LGA, by cluster, by arm :

$$\frac{\text{Number of participants with endpoint}}{\text{Number of participants responding to the HHS}}$$

When used for the analyses, it will be affected to all participant belonging to the same ward, under the likely hypothesis that all participant in the ward area do not attend another ward.

We will estimate the baseline ICC and its 95% CI from our data by performing various calculations using the R ICCbin library⁷ or R ICCest library. First, we will use the Anova estimator (option R ICCbin ci.type=aov), that is originally proposed for continuous data but that is also used for binary data⁸. Then, we will use the Fleiss-Cuzick estimator that is a kappa-type estimator (option R ICCbin ci.type=fc) and the Pearson estimator that is based on direct calculation of the correlation between observations within each cluster (option R ICCbin ci.type=peq). If the results are different, we will keep the more conservative calculation, so the highest ICC estimator.

If necessary, we will refine thereafter the sample size of the endline cross-sectional survey according to the actual intra-cluster correlation coefficient and the baseline measles vaccine coverage proportion results from the baseline HHS survey.

3.1.3 After baseline cross-sectional survey

The following characteristics of clusters collected at the start of SQ-LNS supplementation will be described in NutriVax arm only, globally, between LGA, between LGA*clusters:

- Aggregated data from the SQ-LNS supplementation programme register (NutriVax arm only) : total number of new admissions to the SQ-LNS supplementation program, new ; Total number of new admissions to the SQ-LNS supplementation program, OTP cured ; Total new admissions to the SQ-LNS supplementation program (new and OTP cures), children 6-11 months ; Total new admissions to the SQ-LNS supplementation program (new and OTP cures), children 12-23 months ; Total number of children discharged from the SQ-LNS supplementation program ; Total number of sachets of SQ-LNS distributed ; Total Number of days out of stock of SQ-LNS.
- Aggregated data from the child immunization register (both arms): total doses of different vaccines, total number of days of stock of measles vaccines and others vaccines.

3.2 SURVEY PARTICIPANTS CHARACTERISTICS

The following participant characteristics will be described both for the longitudinal study, for the cross-sectional baseline survey and for the endline cross-sectional survey, by arms, by LGA, by LGA*arm*clusters.

No adjustment for clustering will be applied when summarising the baseline characteristics.

3.2.1 Respect of eligibility criteria

Analyses to be done in order to check compliance with the eligibility criteria are described below.

- Inclusion criteria for the baseline and for the endline surveys:
 - **Residence:** check that all the participants residing in the place where the survey is taking place
 - **Age:** check that all the participants are 12-23 months old
 - **Oral consent:** check that oral informed consent form is given by the child's a parent or legal guardian
- Non-inclusion criteria for the baseline and for the endline surveys
 - **Included in the cohort:** check that all participants are not included in the cohort of the longitudinal survey

3.2.2 Characteristics of children participating in the cross-sectional baseline survey

Variables	Modalities
Demographic characteristics	
Age	In months
Sex	Categories
Settlement	Categories
Sibling and number	Binary Yes/No; quantitative
Immunization	
Vaccination card or a family folder	Categories
Different vaccines and doses (BCG, HepB-0, OPV-0, OPV-1, PCV-1, Penta-1, Rota-1, IPV-1, OPV-2, PCV-2, Penta-2, Rota-2, OPV-3, PCV-3, Penta-3, Rota-3, IPV-2, Measles-1, Yellow fever, Meningitis, Measles-2, Vitamin A-1, Vitamin A-2, Other)	Binary Yes/No
Age at which vaccines were administered	In months
Child has received all the vaccines according to caregiver	Categories
Child has received vitamin A supplementation over the last 6 months	Binary Yes/No

Anthropometric data	
Middle upper arm circumference (MUAC)	Quantitative and/or relevant classes
Nutritional edema	Categories
Child breastfeeding	Binary Yes/No
Medical history	
Chronic disease	Binary Yes/No
Allergies	Binary Yes/No
Hospitalization event in the last 3 months	Binary Yes/No
Child has received deworming supplementation over the last 6 months	Categories
Child currently receiving treatment with RUTF	Binary Yes/No
Child currently receiving treatment with RUSF	Binary Yes/No
Actual medical problem	
Fever in the last 24 hours	Binary Yes/No
Current presence of different pathologies (non-bloody diarrhoea, suspected anaemia, suspected malaria, respiratory infection, vomiting, dehydration, parasitosis, dermatosis, upper respiratory infection, non-malarial fever, abscess, other)	Binary Yes/No
Number of days with different pathologies	Quantitative

3.2.3 Characteristics of families of children participating in the baseline cross-sectional survey

Variables	Modalities
Family demographic characteristics	
Number of people in the household	Quantitative
Demographic characteristics of fathers	
Alive	Binary Yes/No
Age	In years and/or relevant classes
Literacy	Binary Yes/No
Main activity	Categories
Native language	Categories
Demographic characteristics of mothers	
Number of births	Quantitative
Alive	Binary Yes/No
Age	In years and/or relevant classes
Literacy	Binary Yes/No
Main activity	Categories
Marital status	Categories
For married, number of domestic partners	Quantitative
Native language	Categories
Legal representative demographic characteristics	
Accompanist	Categories
Legal representative	Categories

Age	In years and/or relevant classes
Literacy	Binary Yes/No
Education level	Categories
Native language	Categories
Time living in settlement	In months and/or relevant classes
Medical	
Participated in training session for using a MUAC	Binary Yes/No

